5.2 Powered Secondary Endpoint(s)

Imaging Cohort Powered Secondary Endpoints

[REDACTED]

Imaging Cohort Powered Secondary Endpoints are based on the pooled subjects from the Imaging Cohort of Absorb III (■■■■ angiographic subjects and ■■■■ IVUS subjects) and subjects from the Absorb Japan RCT (■■■■ angiographic subjects, and ■■■■ IVUS subjects).

One of the key attributes that differentiates Absorb BVS from metallic stents is the progressive mechanical weakening of the scaffold with polymer degradation over time, which allowed for vessel movement and gradual outward remodeling (positive) to accommodate any increases in the in-scaffold intimal hyperplasia that may limit blood flow. In both the Absorb Cohort A and Cohort B trials, Absorb BVS treated vessels have shown evidence of vessel movement and late lumen and scaffold enlargement, providing anatomic indication that the vessel can adapt and enable the natural Glagov process.²⁴

The vasomotion endpoint assesses the ability of the in-scaffold segment to move when the vessel is no longer mechanically constrained. Angiography will be used for the vasomotion assessment. The assessment of late lumen enlargement will be evaluated by the in-stent/scaffold mean lumen area change (Δ MLA) from post-procedure to 3 years by IVUS.

1. The in-stent/scaffold mean lumen area change, from post-procedure to 3 years by IVUS (mean lumen area measured after nitrate infusions, superiority test, ■■■■ pooled subjects).
2. The in-stent/scaffold mean lumen diameter change, between pre- and post-nitrate infusion at 3 years by angiography (superiority test, ■■■■ pooled subjects).

Powered Secondary Endpoint for Angina

This powered secondary endpoint is intended to assess angina at 1 year and test for superiority of Absorb BVS to XIENCE.

- Angina is defined as the first adverse event resulting in the site diagnosis of angina.
- The analysis will exclude angina following the index procedure through discharge, not to exceed a period of 7 days.

This analysis will include ~2000 subjects.

Powered Secondary Endpoint for All Revascularization

This powered secondary endpoint is intended to assess all revascularization at 1 year and test for superiority of Absorb BVS to XIENCE.

This analysis will include ~2000 subjects.

Powered Secondary Endpoint for Ischemia-Driven Target Vessel Revascularization

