- III. Marked limitation of ordinary activity; for example, angina occurs walking one or two blocks on the level or climbing one flight of stairs in normal conditions and at a normal pace.
- IV. Inability to carry on any physical activity without discomfort - angina syndrome may be present at rest.

CEREBROVASCULAR ACCIDENT/STROKE

Stroke is defined as a sudden onset of focal neurological deficits due to vascular lesions of the brain that persists >24 hours. Any neurological symptom that lasts < 24 hours is classified as TIA. Stroke results from either of two types of cerebral vascular disturbance: ischemia or hemorrhage.

DISCONTINUITY

Use when geometry of an implanted Absorb BVS has perceived or observed discontinuities (such as gaps, breaks or misalignment) on or after (\geq) 6 months post-procedure. Expected by design due to resorption process.

Fracture

When break is suspected to have occurred or reported during use or prior to (<) 6 months post-procedure (whichever is earliest)

DISSECTION

- **National Heart, Lung, and Blood Institute [NHLBI] Dissection Classification System:**
 - A. Minor radiolucencies within the lumen during contrast injection with no persistence after dye clearance.
 - B. Parallel tracts or double lumen separated by a radiolucent area during contrast injection with no persistence after dye clearance.
 - C. Extraluminal cap with persistence of contrast after dye clearance from the lumen.
 - D. Spiral luminal filling defects.
 - E. New persistent filling defects.
 - F. Non-A-E types that lead to impaired flow or total occlusion.

Note: Type E and F dissections may represent thrombus.

VASCULAR COMPLICATIONS (Am Heart J 2003; 145: 1022-9)

Access site injury requiring invasive treatment associated with protocol required procedures and unscheduled cardiac catheterizations. A vascular complication may include access site hematoma, pseudoaneurysm, arteriovenous fistula, peripheral ischemia or nerve injury.

OTHER PROTOCOL SPECIFIC DEFINITIONS

ANGINA

The first adverse event resulting in the site diagnosis of angina.

ASSIGNED DEVICE

In ABSORB III the assigned device for subjects in the Lead-In group is the investigational device Absorb BVS. For subjects in the randomized portion of ABSORB III (including the Imaging Cohort), the assigned device will be either the investigational Absorb BVS or the FDA approved XIENCE V, based on a 2:1 randomization.

BLEEDING CLASSIFICATION

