7.5 Clinical Follow-up for All Subjects

Please see **Protocol Summary** for clinical follow-up schedule and PRO follow-up assessments.

Registered subjects must be clinically followed even if no assigned device is implanted. Clinical follow-up visits must be conducted by a blinded physician, research coordinator, Nurse Practitioner or Physician Assistant who has been trained to the protocol.

For subjects having staged procedures, the follow-up period is considered as having begun upon completion of the original index procedure.

To assess any potential perception bias on the secondary endpoint of percentage of patients who experienced angina within 1 year, information will be collected in a brief patient perception assessment questionnaire administered by the research coordinator post-procedure in the hospital prior to discharge (≥ 4 hours to ≤ 7 days after the procedure) and at 1 year.

The PRO questionnaires will be mailed to the subject for completion or can be completed during the phone or office visit. If questionnaires are mailed to the subjects, the subjects must mail the questionnaires back to the clinical site.

The following information will be collected at each of the time points:

- Any adverse events (including re-hospitalizations)*, repeat coronary angiography, details regarding angina, medications, laboratory tests and 12-lead ECGs, if performed;
- Any angina events
 - If the subject experiences any symptoms of abnormal chest/arm/neck/jaw discomfort or pain, including angina-equivalent or atypical angina pain/sensation, data will be solicited and recorded regarding angina and angina-equivalent symptoms, including the quality, frequency and severity of discomfort/pain, to allow the CEC to adjudicate the symptoms as to angina/angina-equivalent vs. non-angina. This information will be collected by the research coordinator using a standard script. A blinded cardiologist will review the information collected by the research coordinator, provide a diagnosis and sign-off on his/her diagnosis.
- Any repeat coronary angiography and results of such, if applicable;
- Details of any subsequent coronary interventions (e.g., repeat PCI or CABG);
- Use and compliance of medications per clinical investigation plan;
- Use and changes in concomitant cardiovascular medications.

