9. ADJUDICATION OF EVENTS

9.1 The Clinical Events Committee (CEC)

Please refer to **section 9.1** of ABSORB III Protocol ([REDACTED], August 16, 2018) for relevant information on CEC. In addition to the events adjudicated in ABSORB III, in ABSORB IV the CEC will also adjudicate any patient reported symptoms of abnormal chest/arm/neck/jaw discomfort or pain to angina/angina-equivalent vs. non-anginal symptoms.

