APPENDIX II: DEFINITIONS

Please refer to **Appendix II** of ABSORB III Protocol ([REDACTED], March 14, 2017) for complete list of definitions. New or updated definitions are listed below:

MYOCARDIAL INFARCTION (MI)

Protocol MI Definition: Periprocedural MI definition is modified from Moussa ID, Klein LW, Shah B, Mehran R, Mack MJ, Brilakis ES, Reilly JP, Zoghbi G, Holper E, Stone GW. Consideration of a new definition of clinically relevant myocardial infarction after coronary revascularization: an expert consensus document from the Society for Cardiovascular Angiography and Interventions (SCAI). J Am Coll Cardiol. 2013 Oct 22;62(17):1563-70.

This definition will be used for the primary analysis of ABSORB IV and secondary analysis of ABSORB III.

Classification	Biomarker Criteria	Additional Criteria
Periprocedural – patients with a) stable CAD, or b) silent ischemia, or c) acute coronary syndromes with at least 2 baseline troponin values which remained <ULN, or d) acute coronary syndromes in whom the troponin and/or CK-MB levels were elevated but all returned to <ULN prior to the procedure	Absolute CK-MB rises within 48 hours of the procedure to > 5 x ULN for post-PCI or CK-MB > 10 x ULN for post-CABG	Baseline value* < ULN; see also **
Periprocedural – patients with stable CAD and elevated baseline CK-MB, or acute coronary syndromes in whom at least 2 baseline troponin and CK-MB values were drawn and the most recent troponin and CK-MB values were less than the preceding measures by >25%	Absolute incremental CK-MB rise within 48 hours of the procedure from the most recent CK-MB level by > 5 x ULN for post-PCI or > 10 x ULN for post-CABG	

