MI after the periprocedural period may be secondary to late stent complications or progression of native disease. Performance of ECG and angiography supports adjudication to either a target or non-target vessel in most cases.

With the unique issues and pathophysiological mechanisms associated with these later events as well as the documented adverse impact on short and long-term prognosis, a more sensitive definition than for periprocedural MI of any elevation of troponin or CKMB above the 99th percentile of the upper range limit (or ULN if URL is not available) is used. All late events that are not associated with a revascularization procedure will be considered simply as spontaneous.

Myocardial infarctions will also be adjudicated based on the following classification:

- **Q wave MI**

Development of new, pathological Q wave on the ECG (≥ 0.04 seconds in duration and ≥ 1 mm in depth) in ≥ 2 contiguous precordial leads or ≥ 2 adjacent limb leads)

- **Non-Q wave MI**

Those MIs which are not Q-wave MI.

Myocardial infarctions will also be adjudicated as to their relation to the Target Vessel

All infarcts that cannot be clearly attributed to a vessel other than the target vessel will be considered related to the target vessel.

For **Universal** and **WHO MI** definitions, please refer to ABSORB III protocol ([REDACTED], August 16, 2018). These definitions will be used for secondary analysis for ABSORB IV and ABSORB III.

ANGINA

Angina is defined as any angina or angina equivalent symptoms determined by the physician and/or research coordinator after interview of the patient, and as adjudicated by a clinical events committee (CEC).

ADVERSE EVENT [AE]

An adverse event (AE) is any untoward medical occurrence, unintended disease or injury, or untoward clinical signs (including abnormal laboratory findings) in subjects, users or other persons, whether or not related to the investigational medical device.

NOTE 1: This definition includes events related to the investigational medical device or the comparator.

NOTE 2: This definition includes events related to the procedures involved.

NOTE 3: For users or other persons, this definition is restricted to events related to investigational medical devices.

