2. ANALYSIS CONSIDERATIONS

2.1 Statistical Methods

Baseline demographic, clinical, angiographic, procedural, and device data, and treatment results will be summarized using descriptive summary statistics. All data collected will be summarized overall and by treatment arms for ABSORB IV (N=2600) and the pooled population of ABSORB III primary analysis group and ABSORB IV (N=4600).

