2.1.2 Statistics for Categorical Variables

For categorical variables such as gender, MACE, and TVF, results within treatment arm will be summarized with subject counts and percentages/rates, and where specified in the table mockups, with exact 95% Clopper-Pearson³ confidence intervals. Differences between the two treatment arms, when specified, will be summarized with the difference in percents and the Newcombe⁴ score 95% confidence interval for the difference of two percentages.

For efficacy and safety endpoint(s), relative risks (i.e., the ratio of rates), confidence interval for the relative risks, the difference in rates and the confidence interval for difference in rates (using previously-described formulas), and p-values may also be presented for hypothesis generating purposes. The p-values will be based on either Pearson's Chi-square test or Fisher's exact test by checking the expected frequency for each cell in the 2x2 contingency table against Cochran's rule⁶, i.e., if the expected frequencies for all cells are ≥ 5 , then Pearson's Chi-square test will be used, otherwise Fisher's exact test will be used.

For the determination of event rates at all time points (in-hospital, 30 days, 180 days and 1 to 7 (8/9/10) years), the denominators are defined as below based on the type of events.

- Death/MI/Revascularization (DMR) event

Subjects will be included in the analysis if they either had the DMR event by that time or they did not have the DMR event but had follow-up through that time point. In other words, subjects will be included in a given analysis if it can be determined whether or not the subject would have had the DMR event by the time point.

- Stent/Scaffold Thrombosis, Vascular/Bleeding, CVA, and Angina

Subjects will be included in the analysis if they either had the specific event (for example, for analysis on ST, only ST is considered) by that time or they did not have the event but had follow-up through that time point. In other words, subjects will be included in a given analysis if it can be determined whether or not the subject would have had the event by the time point.

Formulas for calculating confidence intervals for the categorical variables are given below.

1. 100(1- α) % Exact Clopper-Pearson Confidence Interval for A Single Proportion³

$$\text{Lower Confidence Limit} = \frac{x}{x + (n - x + 1)F_{1-\frac{\alpha}{2}}(2(n - x + 1), 2x)}$$

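### Read literally, the SAP puts angina into the pooled N=4600 summaries although ABSORB III and ABSORB IV define and ascertain it differently; only descriptive output is affected

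*Protocol*

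**What the plan says.** **ABSORB III.** Protocol section 5.2 (ABSORB III part) states: "Angina is defined as the first adverse event resulting in the site diagnosis of angina". Appendix II of that part gives the same definition: "The first adverse event resulting in the site diagnosis of angina".

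**ABSORB IV.** Appendix II of the ABSORB IV part refers back to the ABSORB III definitions and then says: "New or updated definitions are listed below". Angina is on that list: "Angina is defined as any angina or angina equivalent symptoms determined by the physician and/or research coordinator after interview of the patient", subject to committee adjudication. Ascertainment changes as well. Section 7.5 has symptoms solicited at each follow-up contact: "This information will be collected by the research coordinator using a standard script". Section 9.1 adds committee review of symptoms to the ABSORB III list of adjudicated events: "in ABSORB IV the CEC will also adjudicate any patient reported symptoms of abnormal chest/arm/neck/jaw discomfort or pain to angina/angina-equivalent vs. non-anginal symptoms".

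**Pooling.** SAP 2.1 states: "All data collected will be summarized overall and by treatment arms for ABSORB IV (N=2600) and the pooled population", that population being the ABSORB III primary analysis group plus ABSORB IV, N=4600. SAP 2.2 names the same two populations for the subgroup analyses, which it says are intended for the product's instructions for use. SAP 2.1.2 gives angina its own denominator rule for event rates, in the group "Stent/Scaffold Thrombosis, Vascular/Bleeding, CVA, and Angina".

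**Powered endpoint.** SAP 1.3.2.2 and 1.5.2.2 base the powered angina endpoint on ABSORB IV only.

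**The concern.** An outcome that is asked about with a script and then adjudicated is not the same as one that enters the data when a site records a diagnosis. The number of occasions to detect it also differs: ABSORB IV schedules five contacts through 1 year (30, 90, 180 and 270 days, and 1 year), ABSORB III three (30 and 180 days, and 1 year). Nothing in ABSORB III provides the scripted interview or the committee review, so the ABSORB IV outcome cannot be rebuilt for ABSORB III subjects.

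For myocardial infarction, ABSORB IV Appendix II builds a bridge: its definition is also to be applied to ABSORB III, as a secondary analysis. No readable text does this for angina.

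At stake is the meaning of a pooled angina rate or arm difference, should one be tabulated. It would describe neither definition, and because the two parts use different allocation ratios, the mix of definitions would differ between the arms.

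**Working it through.** **The plan's own angina figure.** SAP 1.5.2.2 states about 99% power with 1235 per arm, a 7% margin and one-sided alpha 0.025. The assumed rates are redacted, so this cannot be fully reproduced. A Farrington-Manning calculation with equal true rates gives 99.1% at a rate of 20%, 98.0% at 25% and 96.7% at 30%; exactly 99% corresponds to a rate of about 20.7%. The stated power is plausible. It concerns ABSORB IV alone and is not in dispute.

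**Inputs for the pooled summary.**
- ABSORB III primary analysis group: 2000 subjects at 2:1, so 1333 Absorb and 667 XIENCE.
- ABSORB IV: 2600 subjects at 1:1, so 1300 and 1300.
- Pooled: 1333 + 1300 = 2633 Absorb and 667 + 1300 = 1967 XIENCE, total 4600.

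**Share of each pooled arm that comes from ABSORB III.**
- Absorb: 1333/2633 = 50.6%.
- XIENCE: 667/1967 = 33.9%.
- Difference: 16.7 percentage points.

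**Crude pooled difference with no device effect.** Let r3 and r4 be the angina rates in ABSORB III and ABSORB IV, each the same in both arms. Then

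- pooled Absorb = 0.506 r3 + 0.494 r4
- pooled XIENCE = 0.339 r3 + 0.661 r4
- Absorb minus XIENCE = (0.506 - 0.339)(r3 - r4) = 0.167 x (r3 - r4)

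The documents give no angina rate for either trial. The rates below are assumptions, chosen to show the range and both signs.

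| Assumed r3 | Assumed r4 | Pooled Absorb | Pooled XIENCE | Difference (points) |
|---|---|---|---|---|
| 20% | 20% | 20.0% | 20.0% | 0 |
| 15% | 20% | 17.5% | 18.3% | -0.84 |
| 15% | 25% | 19.9% | 21.6% | -1.67 |
| 20% | 35% | 27.4% | 29.9% | -2.51 |
| 25% | 20% | 22.5% | 21.7% | +0.84 |

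**Effect of stratifying.** In every row the difference within each trial is zero, so any weighted average of the two within-trial differences is also zero. A trial-stratified estimate removes the whole shift. What it leaves is a figure that averages effects on two differently defined outcomes.

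**The case against.** The strongest reply is that no pooled angina table is named anywhere. Every readable passage that specifies an angina analysis confines it to ABSORB IV, and the only pooled endpoint named explicitly is TLF through 5 years (Protocol, ABSORB IV section 5.3). The subgroup sections list adverse event data among their outputs, not the angina endpoint by name. This stands: the pooling follows from a general rule, not from an explicit plan for angina. But the rule covers all data, angina is one of the event types to which the SAP's rate rules apply, and nothing readable excludes it.

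Second, the text where an exception would sit cannot be read. Nothing is legible between SAP 2.3 and 2.11, and the pooling-strategy heading at Protocol 10.4.11 (ABSORB IV part) has no visible text. This also stands; a harmonisation rule may exist there.

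Third, the quantified shift comes from crude pooling across unequal allocation ratios. It would affect any endpoint whose rate differs between the trials, and stratification cures it. That is correct. The part specific to angina is the mixture of definitions, which has no number attached.

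Fourth, these outputs are descriptive. SAP 2.1.2 presents p-values for event comparisons as hypothesis-generating, and SAP 2.2.3 disclaims confirmatory inference for its subgroups. That limits the weight of the point but does not make the pooled figure interpretable.

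**Conclusion.** The point holds as a matter of descriptive output. Under the readable rule, angina enters the pooled summaries with two definitions and unequal arm weights, and a crude arm difference moves by 0.167 points for each point of between-trial rate gap even when the devices are equivalent. The calculation assumes exact 2:1 and 1:1 allocation, the planned sample sizes with no loss to follow-up, and unstratified pooling.

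Three stronger readings are tempting, and the documents do not support them.
- A reader might infer that the powered angina test is compromised. It is not: it uses ABSORB IV subjects under one definition.
- A reader might infer that the shift favours Absorb, on the view that scripted questioning finds more angina. Committee adjudication can also remove events, no rates are given, and the sign reverses if the ABSORB III rate is the higher one.
- A reader might set the shift against the 7% non-inferiority margin. That margin belongs to the ABSORB IV test; no pooled angina test or margin is stated.

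**What to change.** State in SAP 2.1 and 2.2 that angina under the trial-specific definitions is reported within each trial and left out of the N=4600 tables.

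If a pooled line is wanted, use one definition available in both trials. A site-diagnosed angina adverse event through 1 year is a candidate, because section 8.3.1 of both protocol parts collects all adverse events to that point. Label it as such and stratify the arm comparison by trial. A common definition does not equalise the number of contacts or the scripted questioning, so the table should carry a note on ascertainment.

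If redacted SAP text already contains such a rule, a cross-reference from 2.1 and 2.2 is enough.

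The cost of the first option is a sentence in each of the two sections and the removal of angina from the pooled tables. No data are lost, since each trial still reports its own angina result, and neither the sample size nor the powered analysis changes. The second option adds one derived variable and one stratified summary.

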APPENDIX III: SCHEDULE OF EVENTS

PROCEDURE/TEST	Baseline	Baseline (within 7 days)	Pre-Procedure (within 48 hours)	Procedure	Post-Procedure	30 ±7d, 90 ±14d, 180 ±28d, 270 ±28d Telephone contact or office visit	14 months ± 1 month	1, 2, 3, 4, 5 yrs (± 28 d), Telephone contact or office visit	62 months ± 1 month	Unscheduled visits
Subject Medical/Clinical History (Age, Sex, Risk Factors, Angina Status, Cardiac History)	✓									
Subject Informed Consent (Must be obtained prior to any study related testing or procedures)	✓									
General Inclusion/Exclusion Criteria ¹¹	✓									
Angiographic Inclusion/Exclusion Criteria				✓ ⁷						
Pregnancy Test (if applicable)		✓								
Hgb, Platelet Count, Creatinine, HbA1c, eGFR, WBC	✓ ¹									
CK and CK-MB			✓ ²	✓ ³	✓ ⁴					✓ ⁷
Troponin I or T			✓ ²	✓ ³						✓ ⁷
12-lead ECG			✓ ⁵		✓ ⁵					✓ ⁷
Coronary Angiogram				✓ ⁸						
Study device information				✓						
Per Protocol Medications ⁶			✓	✓	✓	✓		✓		✓
Concomitant Medications	✓			✓	✓	✓		✓		✓
Adverse Events				✓	✓	✓		✓		✓
Patient Reported Outcome Instruments	✓ ⁹					✓ ¹⁰		✓ ¹⁰		
Patient Perception Questionnaire					✓ ¹²			✓ ¹²		
SPECT ¹⁴							✓			✓ ¹⁵
CT Angiogram/Perfusion ¹⁴					✓ ¹³				✓	✓ ¹⁵

1. The 21 day lab result must be known prior to index procedure. HbA1c is to be collected in diabetic subjects only, and its result is not needed prior to the index procedure.
2. All patients admitted with the diagnosis of possible acute coronary syndrome (including unstable angina, NSTEMI or STEMI) must have at least one and preferably 2 or more complete sets of biomarkers (a set consisting of troponin (I or T), CK and CK-MB) measured within 24 hours of procedure. Measurements should be at least 6 hours apart if multiple measurements are taken. If the patient has stable coronary artery disease, the pre-procedure CK and CK-MB must be drawn, but can be obtained during the procedure from the arterial sheath but prior to any angioplasty.
3. During the procedure, all patients with ACS (including unstable angina, NSTEMI or STEMI) must have troponin, CK and CK-MB drawn from the arterial sheath prior to first balloon inflation. For patients with stable coronary artery disease, it is strongly recommended to have a CK and CK-MB drawn from the arterial sheath prior to the first balloon inflation.
4. At least two post-procedure draws required: 1) 6-12 hours post-procedure; 2) 18-24 hours post-procedure or at the time of discharge as long as discharge is at or after 16 hours post-procedure (for hospitals required to discharge stable subjects prior to 16 hours, the subject may be discharged but will have to return to the enrolling institution for their second biomarker draw). If either of the post-procedure CK-MB levels are ≥ 5 x ULN, serial CK and CK-MB levels must be drawn until they are falling.

5. Pre-procedure ECG preferred to be done within 24 hours. Post-procedure ECG must be done within 24 hours post-index procedure.
6. Refer to body of the protocol for details regarding pre-procedure antiplatelet loading requirements. Post-procedure: prasugrel 5 or 10 mg daily, clopidogrel a minimum of 75 mg daily or ticagrelor 90 mg twice daily, must be given for a minimum of 12 months, and Aspirin ≥ 75 mg to ≤ 100 mg daily must be taken through 5 years follow up (potentially up to 10 years follow-up) during the study, and should continue to be taken indefinitely. If a subject develops hypersensitivity to clopidogrel, prasugrel or ticagrelor, subject may be switched to ticlopidine at a dose in accordance with standard hospital practice.
7. For unscheduled visits for suspected ischemic cardiac events, sites should make reasonable efforts to obtain cardiac enzymes (Troponin I or T), CK and CK-MB, and/or ECG if the site is aware of the visit at the time of its occurrence. In all other scenarios (i.e., site does not become aware until after the fact), no protocol deviation will be issued if Troponin I or T, CK and CK-MB, and/or ECG were not obtained at the time of the unscheduled visit.
8. Baseline (prior to pre-dilatation) and final (after stenting/post dilatation) angiogram must be obtained and sent to the core laboratory.
9. Every effort should be made to have subjects complete all patient reported outcomes questionnaires (EQ-5D and SAQ-7) prior to the procedure. However, in situations where this is absolutely not possible, subjects may complete them post-procedure, prior to discharge. Subjects who complete their questionnaires post-procedure should base their responses on their condition prior to the procedure.
10. All registered subjects may complete PRO (EQ-5D and SAQ-7) at 30, 180 days, and at 1, 3 and 5 years.
11. LVEF may be obtained within 6 months prior to the procedure for subjects with stable CAD and for ACS patients it must be assessed within 1 week of the index procedure and after ACS presentation, which may include contrast left ventriculography during the index procedure but prior to randomization in order to confirm the subject's eligibility
12. Administered ≥ 4 hours to ≤ 7 days after the procedure, preferably before hospital discharge, and at 1 year follow-up.
13. Baseline CT Angiogram/Perfusion will be performed up to 7 days after the index procedure or staged procedure, whichever occurs last.
14. Only for subjects in the ABSORB-RESOLVE Ischemia Sub-study. The first CT will be conducted between the day of the index or staged procedure, whichever occurs last, up to 7 days after that procedure. The SPECT will be completed at 14 ± 1 month and the second CT will be conducted at 62 ± 1 month.
15. If a subject enrolled in the ABSORB-RESOLVE Ischemia Sub-study has a cardiovascular related unscheduled event, please follow the procedures outlined in section 12.4.2.2 and 12.4.2.3.

[figure not shown]
